3 STUDY DESIGN

This is an open-label, single-institution, Phase 2 study to determine the response rate of BXCL701 administered orally and daily, combined with pembrolizumab, in patients with

advanced solid cancers. The study will also assess other efficacy parameters, such as PFS, OS and DOR, as well as the safety the combined treatment. Bayesian optimal phase 2 (BOP2) design will be adopted to monitor efficacy. The study will consist of 2 stages:

[figure not shown]
- Lead-in Stage (first 6 patients enrolled) in which the safety and tolerability of the combination of BXCL701 administered orally twice a day on Days 1 to 14 of a 21day cycle plus pembrolizumab 200 mg administered intravenously (IV) on Day 1 every 21 days will be assessed and confirmed in patients with advanced solid cancers. The dose of BXCL701 will be 0.6 mg divided in two doses (0.3 mg twice a day).
- 2) Efficacy Stage (BOP2-Stage) in which patients with advanced solid cancers will be treated with BXCL701 combined with pembrolizumab. Patients enrolled to the Lead-in Stage will be also evaluated in the efficacy stage. Starting from Protocol version 7, new patients enrolled will be administered BXCL701 at the starting dose of 0.2 mg orally twice a day for the first 7 days. If well tolerated and in the absence of signs and symptoms of clinically significant hypotension the dose will be escalated to 0.3 mg orally twice a day.

During the Lead-in Stage, patients will be observed for dose-limiting toxicity (DLT) during Cycle 1. Six patients will be treated initially with 0.3 mg BXCL701 twice a day (Days 1 to 14) plus pembrolizumab 200mg:

- If > 1 of the 6 original patients has a DLT in Cycle 1, the dose will be considered above the maximum tolerated dose (MTD) and additional 6 patients will be treated at the 0.4 mg BXCL701 daily Days 1 to 14 dose level.
 - If ≤ 1 of the patients experience a DLT, the Efficacy Stage can commence
 - \circ If > 1 of the patients experience a DLT, a discussion will be held between the investigators and supporters as to how to proceed

The study schema is presented in Figure 1.

DLT = dose-limiting toxicity; pembro = pembrolizumab; PR, partial response; CR, complete response

All safety data from all patients, who received at least one dose of study drug will be included in safety analysis. Unless doses were held because of DLT, a patient must have

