received >70% of their BXCL701 in Cycle 1 (i.e., \geq 30 of 42 planned doses) with pembrolizumab dosed on Day 1 of Cycle 1 to be eligible for DLT assessment.

Toxicities will be assessed by the investigator using the National Cancer Institute Common Terminology Criteria for Adverse Events (NCI CTCAE), version 5. The relationship of an AE to combination therapy (i.e., attribution to BXCL701 and/or pembrolizumab) is to be assessed by the investigator using the criteria in the protocol (Section 5.3.1).

A DLT is defined as any of the following AEs occurring during Cycle 1, regardless of investigator attribution to study treatment, unless the AE can be clearly and incontrovertibly attributed to an extraneous cause (e.g., disease progression) by the Principal Investigator:

- Any Grade 4 laboratory abnormality, regardless of duration.
- Any Grade 3 laboratory abnormalities if associated with clinical symptoms regardless of duration
- Any Grade ≥3 non-hematologic AE, with the exceptions of Grade ≥3 nausea, vomiting, diarrhea, constipation, and fatigue, that resolves to Grade ≤1 within 72 hours with optimal medical management and/or supportive measures.
- Grade ≥3 thrombocytopenia with Grade >1 bleeding or requirement for platelet transfusion.
- Grade \geq 3 febrile neutropenia.
- Grade ≥ 3 fever.
- Grade ≥ 3 skin rash.
- Laboratory abnormalities meeting Hy's law criteria (aspartate aminotransferase [AST] or alanine aminotransferase [ALT] >3 × upper limit of normal [ULN] with concomitant total bilirubin >2 × ULN).
- Any toxicity resulting in \geq 30% held/skipped doses of BXCL701 during Cycle 1.
- Delay of Cycle 2 by ≥ 14 days due to toxicity.
- Any other significant toxicity considered by the investigator and supporter's medical representatives to be dose-limiting.

Efficacy Stage:

After assessment of the safety and confirmation of the BXCL701/pembrolizumab2 dose schedule to be used in the subsequent stage, the Efficacy Stage will begin. Eligible patients will receive oral BXCL701 daily on Days 1 to 14 of a 21-day cycle plus pembrolizumab 200 mg administered IV on Day 1 every 21 days.

Study Design Features (Both Stages):

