- p. Pregnancy test for the D1 of the 1st cycle can be skipped if the test for the screening period is performed close to the 1st cycle.
- q. Laboratory assessment for immune-related toxicities will be added as per patient's toxicity and as needed upon the investigator's discretion.
- r. Days 8 and 15 of Cycles 1 and 2 can have a window of \pm 2 days. These visits can be also preformed using the telehealth in case of unanticipated events such as COVID-19 pandemics if in agreement with applicable regulations.
- s. Details about collection and processing are in the Laboratory Manual.
- t. C1D5 visit has a window of -1 day and can happen on C1D4.
- u. T3, FT4 and TSH testing will performed at baseline, C4D1 (±7 days), C7D1 (±7 days), C10D1 (±7 days), and Day 1 (±7 days) of every 3rd cycle thereafter and at EOT.
- v. Hematology (CBC plus differential [5 part or auto-analyzer]), serum chemistry and liver function tests will not be performed on Days 8 and 15 after Cycle 4 (at Cycle 5 and beyond)

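### Appendix A note r allows remote Cycle 1 Day 8 and Day 15 visits without saying that the safety blood tests must still be drawn, and DLT evaluability does not depend on them, so a transient laboratory DLT could go unmeasured

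*Combined protocol and SAP*

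**What the plan says.** **Schedule.** In the Appendix A table, hematology, serum chemistry and liver function tests are marked at screening, Cycle 1 Day 1 (C1D1), C1D8, C1D15 and then C2D1. Days 2, 5 and 14 of Cycle 1 carry none of them. Note r gives Days 8 and 15 of Cycles 1 and 2 a window of ±2 days and adds: "These visits can be also preformed using the telehealth in case of unanticipated events such as COVID-19 pandemics", on condition that regulations permit it. It says nothing about the tests marked on those days.

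**DLT definition (Section 3).** The window is Cycle 1: "A DLT is defined as any of the following AEs occurring during Cycle 1". The list includes "Any Grade 4 laboratory abnormality, regardless of duration", Grade 3 laboratory abnormalities with symptoms, and Hy's law. The thrombocytopenia and febrile neutropenia criteria also involve a blood count.

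**Who is assessed for DLT (Section 3).** Unless doses were held because of a DLT, the patient must have "received >70% of their BXCL701 in Cycle 1", glossed as at least "30 of 42 planned doses", "with pembrolizumab dosed on Day 1 of Cycle 1 to be eligible for DLT assessment". No laboratory result is required, and no rule covers a patient whose panels are missing.

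**Where the count is used.** DLT in the first six patients is a primary objective. The Efficacy Stage opens if at most one of six has a DLT (Section 3). Section 7 suspends accrual if the empirical DLT rate exceeds 33%.

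**The concern.** The two visits that may go remote are the two that carry every in-cycle safety panel after the first dose. A video or telephone visit does not itself yield a blood sample, and the plan names no other place for the draw. If the draw lapses, the evaluability rule does not notice: the patient stays in the denominator and can enter the numerator only through clinical events.

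The error has one direction. An unmeasured panel can hide a DLT but cannot create one. It therefore favours passing the lead-in and lowers the rate compared with the 33% suspension threshold. It would also cluster in periods of disruption, so ascertainment could differ between patients enrolled at different times.

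**Working it through.** There is no plan figure to reproduce; the point rests on reading the schedule, note r and the DLT rules together. The arithmetic below shows only how much could turn on it.

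**1. What C2D1 could recover.** Note c places C2D1 21 days (±3) after the previous dose. I read this as counted from C1D1, which gives Day 22, range 19 to 25. Assume onset equally likely on each of Days 1 to 14, and that an abnormality starting on day *o* and lasting *L* days is seen by a test on day *T* if *o* ≤ *T* ≤ *o* + *L*. Number of the 14 onset days seen:

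| Panel | L = 7 | L = 10 | L = 14 |
|---|---|---|---|
| C2D1 on Day 19 | 3 (21%) | 6 (43%) | 10 (71%) |
| C2D1 on Day 22 | 0 (0%) | 3 (21%) | 7 (50%) |
| C2D1 on Day 25 | 0 (0%) | 0 (0%) | 4 (29%) |
| Days 8 and 15 | 14 (100%) | 14 (100%) | 14 (100%) |
| Days 10 and 17 | 12 (86%) | 14 (100%) | 14 (100%) |

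So C2D1 is a partial substitute at best. The plan also does not say whether a value first seen at C2D1 counts as a Cycle 1 DLT.

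**2. Lead-in pass probability.** Inputs: six patients and a pass at 0 or 1 DLT (Section 3). Assumed, because the documents give none of them: true DLT rate *p*; share *s* of DLTs visible only on a laboratory panel; number *k* of the six patients with neither panel drawn; fraction *d* of laboratory-only DLTs still caught and counted at C2D1.

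Observed DLT probability in a remote patient: *r* = *p* × [1 − *s* × (1 − *d*)]. 
P(pass) = P(0 among *k*) × P(0 among 6 − *k*) + P(1 among *k*) × P(0 among 6 − *k*) + P(0 among *k*) × P(1 among 6 − *k*).

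All panels drawn, *p* = 0.30: 0.7⁶ + 6 × 0.3 × 0.7⁵ = 0.1176 + 0.3025 = **0.420**.

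Two remote, *s* = 0.25. For the other four patients, P(0) = 0.7⁴ = 0.2401 and P(1) = 4 × 0.3 × 0.7³ = 0.4116.
- *d* = 0: *r* = 0.225; P(0) = 0.775² = 0.6006; P(1) = 2 × 0.225 × 0.775 = 0.3488. P(pass) = 0.1442 + 0.0837 + 0.2472 = **0.475**.
- *d* = 0.5: *r* = 0.2625; P(0) = 0.5439; P(1) = 0.3872. P(pass) = 0.1306 + 0.0930 + 0.2239 = **0.447**.

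Range with *d* = 0:

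| True rate | All measured | 2 remote, s = 0.25 | 2 remote, s = 0.50 | 6 remote, s = 0.50 |
|---|---|---|---|---|
| 0.30 | 0.420 | 0.475 | 0.532 | 0.776 |
| 0.33 | 0.358 | 0.414 | 0.473 | 0.741 |
| 0.40 | 0.233 | 0.287 | 0.346 | 0.655 |

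Extreme corner, with all six remote and every DLT laboratory-only, *p* = 0.30: *d* = 0.50 gives *r* = 0.15 and P(pass) = 0.776; *d* = 3/14 gives *r* = 0.0643 and P(pass) = 0.948.

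**3. Dose count in the same evaluability sentence.** Section 3 schedules the lead-in twice daily on Days 1 to 14: 14 × 2 = 28 doses. The sentence counts 42, which is 21 × 2. A minimum of 30 exceeds the 28 doses planned, whereas 70% of 28 is 19.6. The percentage and the count cannot both describe that schedule.

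**The case against.** The strongest reply is that nothing cancels the tests. Note r changes how the visit is held, and the Day 8 and Day 15 columns still mark the panels. Where the protocol drops tests it says so: note i excuses repeats when C1D1 follows screening within 72 hours, and note v ends the Day 8 and Day 15 panels after Cycle 4. A reader might infer that telehealth patients have no Cycle 1 laboratory data, or that the plan scores a missing test as no DLT. Neither is written. The gap is silence on both points, and this part of the objection stands.

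Other parts also stand. Telehealth is a conditional exception, not routine. Two of the laboratory-related criteria require clinical signs: symptoms for Grade 3 abnormalities, and bleeding or transfusion for thrombocytopenia. Days 2 and 5 have physical examinations, safety calls are scheduled on Days 3–4 and 6–14, and note q allows added tests for immune-related toxicity, so symptomatic events have other routes to detection. Section 3.1 describes the characteristic BXCL701 events as edema, hypotension, dizziness and hypovolemia, which are clinical. The IND Office must also approve the move to the Efficacy Stage and could query missing panels.

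These narrow the exposure to transient, asymptomatic Grade 4 values and biochemical Hy's law events. They do not close it. Calls and examinations do not reveal a silent laboratory abnormality, and the IND Office has no written criterion for rejecting a patient without panels.

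**Conclusion.** The gap is real but limited. The plan neither requires the Day 8 and Day 15 panels when the visit is remote nor makes DLT evaluability depend on them. A patient without either can enter the one-in-six rule, and the numerator and denominator of the 33% rule, as DLT-free on laboratory criteria.

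The direction is certain; the size is not. With an assumed true rate of 0.30, two of six patients remote and a quarter of DLTs laboratory-only, the lead-in pass probability moves from 0.42 to about 0.45–0.48. A reader might reach 0.78–0.95 instead. Those values need all six patients remote and every DLT visible only in the laboratory, an extreme case that nothing in the documents supports. For the 33% rule I give no figure, because Section 7 states neither its denominator nor when it is applied.

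The documents do not show whether the lead-in is complete. If it is, the point still bears on Efficacy Stage monitoring. It deserves a change and not just a clarifying note, because it settles who counts in a primary endpoint and a safety rule.

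**What to change.** 1. **Appendix A, note r:** state that when a Cycle 1 Day 8 or Day 15 visit is held remotely, the hematology, chemistry and liver tests scheduled for that day are still drawn, and that a local laboratory is acceptable.
2. **Section 3, DLT evaluability:** add that a patient without a DLT who lacks both post-baseline Cycle 1 safety panels is not DLT-evaluable and is replaced. A patient who has had a DLT stays in the count whether or not panels exist.
3. **Same sentence:** reconcile the 42-dose count with the 28 doses that the Section 3 lead-in schedule implies, since the evaluability rule cannot be applied while the two disagree.

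Cost: three short text edits and no new test, because the draws are already scheduled. The downside is local-laboratory logistics for remote patients and an occasional replacement.

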13 APPENDIX B: RESPONSE EVALUATION CRITERIA IN SOLID TUMORS (RECIST) VERSION 1.1

Adopted from the bibliographic reference [20].

13.1 Measurability of tumor at baseline

At baseline, tumor lesions/lymph nodes will be categorized measurable or non-measurable as follows. Measurable lesions must be accurately measured in at least 1 dimension (longest diameter in the plane of the measurement to be recorded) with a minimum size of:

- 10 mm by CT scan (CT scan slice thickness no greater than 5 mm).
- 10 mm caliper measurement by clinical exam (lesions which cannot be accurately measured with calipers should be recorded as non-measurable).
- 20 mm by chest X-ray.

Malignant lymph nodes: To be considered pathologically enlarged and measurable, a lymph node must be ≥ 15 mm in short axis when assessed by CT scan (CT scan slice thickness recommended to be no greater than 5 mm). At baseline and in follow-up, only the short axis will be measured and followed.

Non-measurable lesions are all other lesions, including small lesions (longest diameter <10 mm or pathological lymph nodes with ≥ 10 to <15 mm short axis), as well as non-measurable lesions.

Response criteria	Evaluation of target lesions
CR	Disappearance of all target lesions. Any pathological lymph nodes (whether target or nontarget) must have reduction in short axis to <10 mm.
PR	At least a 30% decrease in the sum of diameters of target lesions, taking as reference the baseline sum diameters.
PD	At least a 20% increase in the sum of diameters of target lesions, taking as reference the smallest sum on study (this includes the baseline sum if that is the smallest on study). In addition to the relative increase of 20%, the sum must also demonstrate an absolute increase of at least 5 mm. (Note: the appearance of 1 or more new lesions is also considered progression).
SD	Neither sufficient shrinkage from the baseline study to qualify for PR nor sufficient increase to qualify for PD, taking as reference the smallest sum diameters while on study.

13.2 Response criteria

Abbreviations: CR=complete response; PD=progressive disease; PR=partial response; SD=stable disease.

13.3 Evaluation of best overall response

Time point response: At each protocol specified time point, a response assessment should occur. Table below provides a summary of the overall response status calculation at each time point for patients who have measurable disease at baseline.

Target lesions	Non-target lesions	New lesions	Overall response
CR	CR	No	CR
CR	Non-CR/non-PD	No	PR
CR	Not evaluated	No	PR
PR	Non-PD or not all evaluated	No	PR
SD	Non-PD or not all evaluated	No	SD
Not all evaluated	Non-PD	No	Inevaluable
PD	Any	Yes or No	PD
Any	PD	Yes or No	PD
Any	Any	Yes	PD

Table: Response in patients with target disease

Abbreviations: CR=complete response; PD=progressive disease; PR=partial response; SD=stable disease.

13.4 Duration of response

The duration of overall response is measured from the time measurement criteria are first met for CR/PR (whichever is first recorded) until the first date that recurrent or PD is objectively documented (taking as reference for PD the smallest measurements recorded on study).

The duration of overall CR is measured from the time measurement criteria are first met for CR until the first date that recurrent disease is objectively documented.

Stable disease is measured from the start of the treatment until the criteria for progression are met, taking as reference the smallest sum on study (if the baseline sum is the smallest, this is the reference for calculation of PD).

14 APPENDIX C: RESPONSE EVALUATION CRITERIA IN SOLID TUMORS FOR IMMUNE-BASED THERAPIES (iRECIST)

Adopted from the bibliographic reference [19].

14.1 Comparison of response evaluation criteria in solid tumors (RECIST) 1.1 and modified response evaluation criteria in solid tumors for immune-based therapies (iRECIST)

	RECIST 1.1.	iRECIST
Definitions of	Measurable lesions are ≥ 10	No change from RECIST
measurable and non-	mm in diameter (≥ 15 mm for	1.1; however, new lesions
measurable disease;	nodal lesions); maximum of	are assessed as per
numbers and site of	5 lesions (2 per organ); all	RECIST 1.1 but are
target disease	other disease is considered	recorded separately on the
	non-target (must be ≥10 mm	case report form (but not
	in short axis for nodal	included in the sum of
	disease)	lesions for target lesions identified at baseline)
Complete response,	Cannot have met criteria for	Can have had iUPD (one
partial response, or	progression before complete	or more instances), but not
stable disease	response, partial response, or	iCPD, before iCR, iPR, or
	stable disease	iSD
Confirmation of	Only required for non-	As per RECIST 1.1
complete response or	randomized trials	
partial response		
Confirmation of stable	Not required	As per RECIST 1.1
disease		
New lesions	Result in progression;	Results in iUPD but iCPD
	recorded but not measured	is only
		assigned on the basis of
		this category if at next
		assessment additional new
		lesions appear or an
		increase in size of new
		lesions is seen ($\geq 5 \text{ mm for}$
		sum of new lesion target or
		any increase in new lesion non-target); the appearance
		of new lesions when none
		have previously been
		recorded, can also confirm
		iCPD

		-
Independent blinded	Recommended in some	Collection of scans (but not
review and central	circumstances - eg, in some	independent review)
collection of scans	trials with progression-based	recommended for all trials
	endpoints planned for	
	marketing approval	
Confirmation of	Not required (unless	Required
progression	equivocal)	_
Consideration of clinical	Not included in assessment	Clinical stability is
status		considered when deciding
		whether treatment is
		continued after iUPD

"i" indicated immune responses assigned using iRECIST.

Abbreviations: iCPD=confirmed progression; iCR=complete response; iPR=partial response; iSD=stable disease; iUPD=unconfirmed progression; RECIST=Response Evaluation Criteria in Solid Tumors

14.2 Assessment of timepoint response using modified response evaluation criteria in solid tumors for immune-based therapies (iRECIST)

Target	Non-target	New	Timepoint	Timepoint response with previous
lesions	lesions	lesions	response	iUPD in
			with no	any category ^a
			previous	
			iUPD in	
			any	
			category	
iCR	iCR	No	iCR	iCR
iCR	Non-iCR/non-	No	iPR	iPR
	iUPD			
iPR	Non-iCR/non-	No	iPR	iPR
	iUPD			
iSD	Non-iCR/non-	No	iSD	iSD
	iUPD			
iUPD with	iUPD with no	Yes	Not	New lesions confirm iCPD if new
no change,	change, or		applicable	lesions were previously identified
or with a	decrease from			and they have increased in size
decrease	last timepoint			$(\geq 5 \text{ mm in sum of measures for })$
from last				new lesion target or any increase
timepoint				for new
				lesion non-target) or number; if no
				change is seen in new lesions
				(size or number) from last
				timepoint, assignment remains
				iUPD
iSD, iPR,	iUPD	No	iUPD	Remains iUPD unless iCPD is
iCR				confirmed on the basis of a further

				increase in the size of non-target
				disease (does not need to meet
				RECIST 1.1 criteria for
				unequivocal progression)
iUPD	Non-iCR/non-	No	iUPD	Remains iUPD unless iCPD is
	iUPD, or iCR			confirmed on the basis of a further
				increase in sum of measures ≥ 5
				mm; otherwise, assignment
				remains iUPD
iUPD	iUPD	no	iUPD	Remains iUPD unless iCPD is
				confirmed based on a further
				increase in previously identified
				target lesion iUPD in sum of
				measures ≥ 5 mm or non-target
				lesion iUPD (previous assessment
				need not have shown unequivocal
				progression)
iUPD	iUPD	Yes	iUPD	Remains iUPD unless iCPD is
				confirmed on the basis of a further
				increase in previously identified
				target lesion iUPD sum of
				measures \geq 5 mm, previously
				identified non-target lesion iUPD
				(does not need to be unequivocal),
				or an increase in the size or
				number of new lesions previously
				identified
Non-iUPD	Non-iUPD or	Yes	iUPD	Remains iUPD unless iCPD is
Or	progression			confirmed on the basis of an
progression				increase in the size or number of
				new lesions previously identified

^a Previously identified in assessment immediately before this timepoint.

Abbreviations: iCPD=confirmed progression; iCR=complete response; iPR=partial response; iSD=stable disease; iUPD=unconfirmed progression; non-iCR/non-iUPD=criteria for neither CR nor PD have been met; RECIST=Response Evaluation Criteria in Solid Tumors.
